#### **Data confidentiality**

- Paper-based records will be kept in a secure location and only be accessible to personnel involved in the study.
- Computer-based files will only be made available to personnel involved in the study through the use of access privileges and passwords.
- Prior to access to any study-related information, personnel will be required to sign statements agreeing to protect the security and confidentiality of identifiable information.
- Wherever feasible, identifiers will be removed from study-related information.

A Certificate of Confidentiality will be obtained, because the research could place the subject at risk of criminal or civil liability or cause damage to the subject's financial standing, employability, or liability.

A waiver of documentation of consent is being requested, because the only link between the subject and the study would be the consent document and the primary risk is a breach of confidentiality. (This is not an option for FDA-regulated research.)

Precautions are in place to ensure the data is secure by using passwords and encryption, because the research involves web-based surveys.

Audio and/or video recordings will be transcribed and then destroyed to eliminate audible identification of subjects.

#### **Subject Confidentiality**

Subject confidentiality will be maintained throughout the study according to applicable guidelines, regulations and IRB requirements. All laboratory samples, study clinical data, and reports of results will de-identify individual subjects. Subjects will be identified by initials, date of birth, gender and subject number only for use in data collection. Published data will provide subject numbers only if needed for clarity of presentation (e.g., in individual event listings). The study will be conducted in accordance with the Declaration of Helsinki. The study will be conducted in accordance with the ICH GCP

guidelines. The sponsor-investigator will comply with all applicable regulatory and legal requirements, ICH GCP guidelines, and the Declaration of Helsinki in obtaining and documenting the informed consent. All protected health information (PHI) will be maintained using a network drive and/or devices secured and managed by University of Pennsylvania. Additionally, if necessary, PHI will also be managed on a University approved third-party computing environment. Should PHI need to be transmitted, a University of Pennsylvania-approved encrypted portable device or University of Pennsylvania-approved secure encrypted file transfer solution will be utilized. The subject and any biological material obtained from the subject will be identified by subject ID and trial identification number. Appropriate measures such as encryption or leaving out certain identifiers will be enforced to protect the identity of subjects.

**Sensitive Research Information\***

Does this research involve collection of sensitive information about the subjects that should be excluded from the electronic medical record?

No

**Subject Privacy**

Privacy refers to the person's desire to control access of others to themselves. Privacy concerns people, whereas confidentiality concerns data. Describe the strategies to protect privacy giving consideration to the following: The degree to which privacy can be expected in the proposed research and the safeguards that will be put into place to respect those boundaries. The methods used to identify and contact potential participants. The settings in which an individual will be interacting with an investigator. The privacy guidelines developed by relevant professions, professional associations and scholarly disciplines (e.g., psychiatry, genetic counseling, oral history, anthropology, psychology).

Information about study subjects will be kept confidential and managed according to the requirements of the Health Insurance Portability and Accountability Act of 1996 (HIPAA). Those regulations require a signed subject authorization informing the subject of the following: Protected health information (PHI) collected from subjects in this study Who will have access to that information and why Who will use or disclose that information The rights of research subjects to revoke their authorization for use of their PHI View of PHI will be limited to individuals at the University of Pennsylvania directly involved in the study. The company donating the study product will not have access to PHI. All electronic PHI will be maintained by using an institutionally secured and managed network drive, institutionally secured and managed devices, and institutionally approved third-party computing environments. Should PHI need to be transferred, it will be done so through the use of a Penn-approved encrypted portable drive or a Penn-approved secure encrypted file transfer solution. In the event that a subject revokes authorization to collect or use PHI, the investigator, by regulation, retains the ability to use all information collected prior to the revocation of subject authorization. For subjects who have revoked authorization to collect or use PHI, attempts will be made to obtain permission to collect at least vital status (i.e. that the subject is alive) at the end of their scheduled study period. Where possible, data will be entered directly into our password protected database, REDCap. All data pertaining to the study will be saved on the Center for Weight and Eating Disorders password-protected server. Paper copies of informed consent, questionnaires, interviews, lab results, and any correspondence will be kept in the case record in locked offices.

**Data Disclosure**

Will the data be disclosed to anyone who is not listed under Personnel?

No

**Data Protection\***

- Name
- Street address, city, county, precinct, zip code, and equivalent geocodes
- All elements of dates (except year) for dates directly related to an individual and all ages over 89
- Telephone and fax number
- Electronic mail addresses
- Social security numbers
- Medical record numbers
  - Health plan ID numbers
  - Account numbers
  - Certificate/license numbers
  - Vehicle identifiers and serial numbers, including license plate numbers
  - Device identifiers/serial numbers
  - Web addresses (URLs)
  - Internet IP addresses
  - Biometric identifiers, incl. finger and voice prints
  - Full face photographic images and any comparable images
  - Any other unique identifying number, characteristic, or code
- None

Does your research request both a waiver of HIPAA authorization for collection of patient information and involve providing Protected Health Information ("PHI") that is classified as a "limited data set" (city/town/state/zip code, dates except year, ages less than 90 or aggregate report for over 90) to a recipient outside of the University of Pennsylvania covered entity?

No

**Tissue Specimens Obtained as Part of Research\***

Are Tissue Specimens being obtained for research?

Yes

**Tissue Specimens - Collected during regular care\***

Will tissue specimens be collected during regular clinical care (for treatment or diagnosis)?

No

**Tissue Specimens - otherwise discarded\***

Would specimens otherwise be discarded?

No

**Tissue Specimens - publicly available\***

Will tissue specimens be publicly available?

No

**Tissue Specimens - Collected as part of research protocol\***

Will tissue specimens be collected as part of the research protocol?

Yes

**Tissue Specimens - Banking of blood, tissue etc. for future use\***

Does research involve banking of blood, tissue, etc. for future use?

Yes

**Genetic testing**

If genetic testing is involved, describe the nature of the tests, including if the testing is predictive or exploratory in nature. If predictive, please describe plan for disclosing results to subjects and provision

of genetic counseling. Describe how subject confidentiality will be protected Note: If no genetic testing is to be obtained, write: "Not applicable."

Confidentiality will be protected. Genetic analyses will be completed by other laboratories without access to identifying information (i.e., they will have identification code numbers only). Subjects' identities will be protected during and after genetics testing with the same high standards as the rest of their data. We will be conducting exploratory testing targeting genes in the areas of metabolism, sleep and circadian (24-hour) rhythms.

## Consent

### **1. Consent Process**

#### **Overview**

Study site staff will be obtaining consent by providing a copy and reviewing the consent with all subjects who may be eligible for the current study. The consent process will occur at the Center for Weight and Eating Disorders located at [name]. Study staff will explain that the subject can choose whether or not he or she would like to participate. Study staff will then go over the consent if the subject decides to participate. Study staff will inform the participant of their right to withdrawal from the study at any point in time. Possible risks and benefits of participating in the trial will be discussed during the informed consent process. If subject decides to participate, he or she will be asked to sign the consent form.

#### **Children and Adolescents**

Not applicable.

#### **Adult Subjects Not Competent to Give Consent**

Not applicable.

### **2. Waiver of Consent**

#### **Waiver or Alteration of Informed Consent\***

No Waiver Requested

#### **Minimal Risk\***

#### **Impact on Subject Rights and Welfare\***

#### **Waiver Essential to Research\***

#### **Additional Information to Subjects**

#### **Written Statement of Research\***

No

If no written statement will be provided, please provide justification

The following documents are currently attached to this item:

*There are no documents attached for this item.*

## Risk / Benefit

#### **Potential Study Risks**

During this study you will be asked questions of a personal nature, such as your weight, age, eating and physical activity habits, and mood. You may experience some discomfort when answering these questions. You may not like all of the foods that we give you which may cause some discomfort.

Additionally, the eating schedule may be difficult to manage at times, and this may cause you some inconvenience. You will experience the inconvenience of wearing the wrist activity recorder and keeping records of your eating behaviors, sleep, and activity throughout the study. For the blood draws, you will experience discomfort on initial insertion of the thin needles (introducer) into a vein on your arm and hand. Bruising may develop at the sites of the needle insertions. Dizziness or fainting is a remote possibility. Local clots may form, and infections may occur, but these are rare. The amount of blood drawn will not significantly reduce your blood volume, although there may be a small decrease in your red blood cell concentration (hematocrit). The total volume of blood drawn will be less than 50 teaspoonsfuls, and this loss is readily restored. Occasionally, mild discomfort may occur from a catheter in your vein. If this happens, we will either change its position or remove it entirely, asking your permission before reinserting it. There may be some bruising when the catheters are removed. You will be asked to apply pressure to the site of each catheter for 10 minutes after its removal. There may be a small scar at the catheter sites that will disappear over the course of several months. This research involves exposure to radiation from the DEXA scans. Therefore you will receive a radiation dose. This radiation dose is not necessary for your medical care and will occur only as a result of your participation in the study. At doses much higher than you will receive, radiation is known to increase the risk of developing cancer after many years. At the doses you will receive, it is very unlikely that you will see any effects from the radiation dose. Risks associated with the fat biopsy include bleeding, bruising, infection, possible scarring, and pain. These risks will be reduced by using a trained physician/nurse practitioner to perform the procedures, local anesthesia to reduce pain, and careful monitoring of the site where the fat cells were taken. For the FSIGT test, a known risk is low blood sugar. We will administer insulin 20 minutes after the glucose is given to you to ensure that your blood sugar returns to normal. As insulin lowers blood glucose, there is a possibility that the insulin will make your blood glucose go too low. Low blood sugar results in sweating, shaking, and mental confusion. We will monitor your blood sugar and give you food or glucose directly into your blood if your blood sugar goes too low. The study involves restraining you from eating for a period of at least 10 hours (overnight) while in the hospital, which may be uncomfortable. During the assessment visits you will be staying in a dimly lit room and will be unable to bring any electronics that will emit any extra light, such as your cell phone. This may be an inconvenience. If you are currently pregnant or become pregnant while in the research study, it is important that you inform the investigator because you will not be able to participate. If you are able to become pregnant, you must be given a pregnancy test during the screening period and at each assessment visit. You are asked to use a medically accepted method of birth control (such as condoms, birth control pills or patches, IUDs, etc.) while you participate in the study. The research may involve risks that are currently unforeseeable. If you are injured, you should inform the treating physician that you are in a research study.

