### Procedures

Participants will be recruited through postings on campus and nearby workplaces, pamphlets to Penn Medicine practices, internet advertisements, and local media appearances. Participants will complete an initial phone screen to determine eligibility and assess availability. Participant responses will be reviewed by the principle investigator and if they appear to be eligible, a screening visit will be scheduled. Study staff will complete a clinical interview assessing typical eating and sleep patterns, weight history, and psychiatric status. Participants will also be asked to complete several self-report questionnaires to assess mood, exercise, sleeping and eating patterns, and to examine psychological constructs related to eating and food. Participants will undergo a medical history and physical, and their weight, height, and waist circumference will be measured. Blood pressure, pulse, fasting blood work (which includes tests for a metabolic panel, fasting glucose, HbA1c, lipid panel, and CBC test), and an EKG will also be performed to exclude diabetes, MetS, and other metabolic or cardiac issues. Participants will receive logs to record food, physical activity, and sleep-wake cycles, as used in our previous studies of NES (135,136) and our R21 study, and an actigraph to wear for 10d. Upon completion, study staff will review their logs and actigraphs, and if they meet inclusion criteria, they will be scheduled to undergo the inpatient baseline assessment. After baseline assessment, participants will be randomized to begin the study with either the daytime or delayed eating condition, and they will receive their first 3d of food. The participants will also receive food, sleep, and exercise logs and actigraphs, which they will use for the study duration. Assessment Overview. Assessments will be conducted at 4 phases: 1) pre-eating condition 1; 2) post-eating condition 1; 3) pre-eating condition 2; and 4) post-eating condition 2 (Table 2). Each assessment will include 28h at the Center for Human Phenomic Science (CHPS) where participants will eat according to a standardized schedule. Participants will observe an overnight fast and arrive at CHPS at 0700h. Weight, height, waist circumference, and blood pressure will be measured. Participants will be asked to complete a series of questionnaires to assess psychological measures related to eating and food. Blood will be drawn at 4h intervals for 24h (0800h, 1200h, 1600h, 2000h, 2400h, 0400h and 0800h) to measure circadian rhythms of leptin, ghrelin, melatonin, cortisol and glucose, and of gene expression (43,90,92,95,98,137). A one-time blood sample will also be drawn for genomic analysis. Fasting levels of glucose, insulin, adiponectin, cholesterol, triglycerides, non-esterified fatty acids (NEFAs) and CRP will be measured at 0800h. At the same 4h intervals (0800h, 1200h, 1600h, 2000h, 2400h, 0400h and 0800h), a saliva sample will be obtained using salivette salivary swabs to collect information on changes to the salivary microbiome. This involves participants placing a cotton swab called a Salivette in their mouth to absorb saliva and placing it back into a small tube to be stored; they will be asked to refrain from using toothpaste, mouthwash, or gum beginning at 11 pm the night before admission for this test. After the initial fasting blood draw at 0800h, indirect calorimetry will assess REE and fuel oxidation (RQ) at 0900h. A standardized breakfast will then be served. Next, body composition will be measured using Dual Energy X-ray Absorptiometer (DEXA). At 1200h, blood will be drawn followed by lunch and harvesting of AT at 1300h. Following the AT procedure, participants will complete three computer-based cognitive tests administered by research staff. An afternoon snack, dinner, and evening snack will be served; the last snack will be consumed by 2100h. Participants will then fast overnight in preparation for the FSIGT, and blood draws will continue every 4h. At 0800h, the FSIGT will occur, followed by breakfast, and then discharge from the CHPS. [name], will be contacted in case of medical emergency. In his absence, we will call the hospital operator at [contact] and ask to speak to the endocrinology fellow on call. Dietary Plan and Food Distribution. Research staff will deliver meals and snacks from the CHPS metabolic kitchen 2x/wk, pick up uneaten food, and collect and provide new actigraphs. Participants may also choose to pick up food themselves from the metabolic kitchen if they prefer. Menus will accompany the meals, and participants will check off each food item they consume and note any modifications to their meals and snacks. The CHPS staff will provide portion size training at baseline. Participants will purchase their own beverages and record them on their menus. Mean beverage intake, as reported at baseline, will be factored into each participants total

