
actigraphy data to assess sleep-wake onset and offset and minutes of deliberate physical activity. After baseline, the food log will be a menu based on the foods provided to participants along with the sleep and activity questions. Actigraphy. Wrist actigraphs with light sensors (Spectrum Pro, Philips Respironics Healthcare) will be worn continuously on the non-dominant wrist for the study duration (except when bathing). Actigraphy provides an objective, reliable and valid method for assessing circadian activity patterns, sleep-wake cycles, and light levels in free-living populations with minimal restriction on normal routines (115). Sleep onset, offset, duration, number of nighttime awakenings, and exercise bouts will be determined by actigraphy and confirmed by logs. Inpatient Assessments At each assessment, we will measure weight (kg), height (cm), blood pressure, and waist circumference (see section C.4b.). Participants will also be given a urine drug test and pregnancy test (with the exception of post-menopausal women and women who have had surgeries or treatments, such as a hysterectomy, that make them infertile). Intravenous Placement & Blood Draws for Hormones. Participants will arrive at 0700h at the CHPS and be housed in a 20 lux room (to avoid suppression of melatonin secretion). They will be placed in a supine position and an indwelling intravenous catheter will be inserted at 0730h. Blood draws of 10 ml for hormones will occur every 4h at 0800h, 1200h, 1600h, 2000h, 2400h, 0400h and 0800h. This sampling interval schedule strikes a balance between allowing for detection of circadian phase and amplitude of leptin, ghrelin, melatonin, cortisol and glucose, relative to food intake and sleep, as we and others have documented with circadian cosinor analyses (43,137). Cholesterol, triglycerides, glucose, insulin, adiponectin, NEFAs and CRP will also be measured from the initial fasting blood draw at 0800h on the first morning. No eating will be allowed after 2300h the night before and the night of the assessment. For hormones, blood will be collected in pre-cooled vacutainer tubes containing EDTA and kept on ice until centrifugation at 4°C and then stored at -80°C. Serum will be pipetted into tubes before freezing. Assays will be performed in duplicate by the Penn Diabetes Research Center Radioimmunoassay & Biomarkers Core. Blood Draws for Transcriptomics. 2.5ml whole blood samples also will be collected every 4h at 0800h, 1200h, 1600h, 2000h, 2400h, 0400h and 0800h, into PAXgene Blood RNA tubes (PreAnalytix). This sampling interval schedule allows for detection of the amplitude and circadian phase of gene expression, as has been documented with circadian cosinor analyses (90,98). The PAXgene tubes contain a reagent that helps lyse blood cells to release total RNA and stabilizes the in vivo gene transcription profile by preventing in vitro RNA degradation in blood. The blood will be mixed with this reagent by gently inverting the tube 8-10 times and then will be kept upright at room temperature (18°C to 25°C) for a minimum of 2h and a maximum of 72h. Next, the tubes will be transferred to a -20°C freezer for 24h, and then to an -80°C freezer for storage. An additional 10mL of blood will be collected during the first assessment visit and saved and stored as whole blood. This sample will later be analyzed for the entire genome to provide the researchers with more complete information as to how all genes may contribute to metabolism, sleep and circadian (24-hour) rhythms, an important area of interest to our research. Energy Expenditure. After completion of the first blood draw, participants will remain in bed in a fasted state. At 0900h, resting metabolic rate will be assessed by indirect calorimetry (Parvo Medics TrueOne 2400, Sandy, UT). The Parvo Medics metabolic monitor is an integrated metabolic measurement system which contains O2 and CO2 analyzers, a device for measuring ventilation rates, a gas sampling system, and a computer interface that processes raw data. Resting energy expenditure will be assessed continuously by measuring the volume and the O2 and CO2 concentrations of expired air samples, and will be calculated based on the average VO2 and RQ measures which can be converted to energetic equivalents (kcal/day) (144). Dual Energy X-ray Absorptiometer (DEXA). Following the metabolic testing and breakfast, DEXA (Hologic Discovery Wi Bone Densitometer) will be used to measure total body fat, trunk fat and lean mass (145). AT Biopsies. Using a standard CHPS protocol, subcutaneous white AT will be collected at 1400h by core needle aspiration through a 4-mm gluteal incision and will be treated with RNA Later (Qiagen), snap frozen and stored at -80°C for subsequent RNA extraction (121,122,146,147). Cognitive Inhibition Test Battery. We will use a computer-based battery of tests to assess three aspects of inhibition that have been linked with overeating and disordered eating behaviors. The Stop Signal Task (SST) (Logan, 1994) is a well-validated measure of response inhibition that has been used in previous studies and obesity (Mole, 2015; Svaldi, 2014). Participants respond to left and right-facing arrows (go signal) on the computer screen. On 25% of trials of the 64-trial task blocks, a stop signal (an 800-Hz, 100-ms, 70-dB tone) is presented indicating that response should be inhibited. The initial stop delay in each block is 250ms and adjusts ±50ms depending on whether the participant successfully inhibits (Logan, 1994). The primary outcome is stop signal reaction time (SSRT), calculated as the mean RT on go-trials minus mean stop delay. The Stroop Test is a well-validated measure of interference control, or the ability to suppress habitual responses when shown a colored word and being asked to press the key associated with the color of the word rather than the word itself (Stroop 1935). Higher interference scores are associated with obesity (Cohen, 2011; Fagundo, 2012)

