**Frequently-Sampled Intravenous Glucose Tolerance (FSIGT) Test.** The FSIGT will occur in the CHPS on the second morning at 0800h (with glucose injection) after an 11h overnight fast (participants will stop eating by 2100h the night before). Following baseline blood sampling of 4mL at -15, -10 and -5 minutes, 0.3 g/kg of 50% glucose will be injected over 1 min starting at t=0 and 0.03 U/kg of insulin (1 U/1 ml solution) will be injected over 30 sec starting at t = 20 min. Additional 4mL blood samples will be collected at t=2, 3, 4, 5, 6, 8, 10, 12, 14, 16, 18, 20, 22, 25, 30, 40, 50, 70, 100, 140, and 180 min after the injection of glucose (123,148). Plasma glucose will be determined in duplicate by the glucose oxidase method using an automated glucose analyzer (Hitachi 912i; Roche Diagnostic Systems). Plasma insulin will be measured in duplicate by double-antibody radioimmunoassays (Millipore, Billerica, MA) at the Penn Diabetes Research Center Radioimmunoassay & Biomarkers Core. Free fatty acids (FFA) will be measured in duplicate using enzymatic colorimetrics (Wako Chemicals, Richmond, VA). Each participants samples from all 4 FSIGT tests will be assayed simultaneously. The FSIGT parameters, acute insulin response to glucose (AIRglu), insulin sensitivity (SI), glucose effectiveness (SG), and disposition index (DI), will be derived from Bergmans minimal model using MINMOD Millennium software (version 6.02; 149). AIRglu, a measure of first-phase insulin secretion, is calculated as the incremental area under the curve (AUC) for insulin between 0 and 10 min after injection of glucose. SI, a measure of the capacity of insulin to promote glucose disposal, is modeled from the relationship of incremental insulin values over baseline to glucose disappearance. SG, a measure of the capacity of glucose to mediate its own disposal, is modeled from the effect of basal insulin levels on glucose kinetics. DI is a composite measure of -cell function that accounts for the relationship between insulin secretion and sensitivity by the product of AIRglu and SI, providing an assessment of the appropriateness of -cell compensation for changes in insulin sensitivity. The FFA profile during the FSIGT will be analyzed according to the model of Sumner et al. (150), in which 3 phases of FFA dynamics have been described during the 180 min after the injection of glucose; an extension of basal levels until the initial sustained decrease in FFA; the suppression of FFA until nadir evaluated by the fractional disposal rate; and the time from nadir to return to basal levels as also reported by our group (123). **Transcriptomics of Blood and AT.** The Wistar Institute Genomics Facility will process blood and AT for transcriptomics using standard protocols in place. Total RNA will be isolated from whole blood collected in PAXgene Blood RNA tubes (see section C.6b.) using PAXgene Blood miRNA kits (Qiagen), and Total RNA will be isolated from AT using Direct-zol RNA Miniprep kits (Zymo Research). Extracted RNA will undergo extensive quality control with the Agilent Bioanalyzer 2100 (Agilent), and Qubit fluorometric quantitation (Life Technologies) will be used to obtain accurate RNA concentrations before library preparation. QuantSeq 3mRNA-Seq Library Preparation Kits (Lexogen) will be used for library construction and KAPA Library Quantification Kits will be used for qPCR-based quantification of libraries. Library quality control will be performed with the Agilent Technology 2100 Bioanalyzer using a High Sensitivity DNA chip. Libraries will be pooled and then undergo high-throughput sequencing using the Illumina NextSeq 500.

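### The risk section gives a total blood volume under 50 teaspoons (about 246 mL), but the sampling schedule adds up to about 744 mL (151 teaspoons), three times as much

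*Combined protocol and SAP*

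**What the plan says.** Under Risk / Benefit, Potential Study Risks, the protocol states: "The total volume of blood drawn will be less than 50 teaspoonsfuls, and this loss is readily restored". Nothing in the sentence limits it to one visit.

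The volumes are set out in Procedures:

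- Number of assessments: "Assessments will be conducted at 4 phases: 1) pre-eating condition 1; 2) post-eating condition 1; 3) pre-eating condition 2; and 4) post-eating condition 2".
- Hormones, at each assessment: "Blood draws of 10 ml for hormones will occur every 4h at 0800h, 1200h, 1600h, 2000h, 2400h, 0400h and 0800h".
- Transcriptomics, at each assessment: "2.5ml whole blood samples also will be collected every 4h at 0800h, 1200h, 1600h, 2000h, 2400h, 0400h and 0800h".
- FSIGT baseline: "Following baseline blood sampling of 4mL at -15, -10 and -5 minutes".
- FSIGT after the glucose injection: "Additional 4mL blood samples will be collected at t=2, 3, 4, 5, 6, 8, 10, 12, 14, 16, 18, 20, 22, 25, 30", followed by six more time points (40, 50, 70, 100, 140 and 180 min).
- One further 10 mL whole-blood sample for genomic analysis, at the first assessment only.
- Screening laboratory tests (metabolic panel, lipids, CBC, HbA1c), with no volume given.

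The FSIGT text refers to four tests per participant, so the test is repeated at every assessment. The Study duration section puts a 2-week washout between the two eating conditions, so assessments 2 and 3 are about two weeks apart.

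**The concern.** The stated limit and the schedule are in the same document and cannot both be right as worded. The limit appears in the section on the risks of taking part in the whole study. The sentence that carries it also reassures the participant that the loss is quickly made good. The Risk / Benefit Assessment then refers the reader to that section in support of its minimal-risk judgement.

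If the figure is wrong as a total, anyone relying on the risk text sees about one third of the volume that the schedule draws. Nobody is told the cumulative amount, or that two full assessments fall about two weeks apart. What is at stake is the accuracy of risk disclosure, not the trial's inference.

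**Working it through.** **The plan's own figure.** At 4.929 mL per teaspoon, 50 × 4.929 = 246 mL. At a rounded 5 mL per teaspoon it is 250 mL.

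**One assessment, from Procedures**

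- Hormones: 7 × 10 mL = 70 mL
- Transcriptomics: 7 × 2.5 mL = 17.5 mL. The text says these are collected in addition to the hormone draws.
- FSIGT: 3 baseline + 21 post-injection samples = 24; 24 × 4 mL = 96 mL
- Sum: 70 + 17.5 + 96 = **183.5 mL** (37.2 teaspoons)
- First assessment, with the genomic sample: 183.5 + 10 = **193.5 mL** (39.3 teaspoons)

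The fasting lipid, glucose, insulin and related assays are run on the first 0800h draw and add nothing.

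**Whole study**

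- 4 × 183.5 + 10 = **744 mL**
- 744 / 4.929 = 150.9 teaspoons (148.8 at 5 mL)
- Ratio to the stated limit: 744 / 246.4 = 3.02 (2.98 at 5 mL)

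**Can any reading recover the stated total?**

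| Reading | Volume (mL) | Teaspoons | Ratio to limit |
|---|---|---|---|
| One assessment | 183.5 | 37.2 | 0.74 |
| First assessment, with genomic sample | 193.5 | 39.3 | 0.79 |
| Assessments 1 and 2 | 377 | 76.5 | 1.53 |
| FSIGT samples only, four assessments | 384 | 77.9 | 1.56 |
| Hormone draws only, four assessments | 280 | 56.8 | 1.14 |
| All, without the day-2 0800h draw | 694 | 140.8 | 2.82 |
| All, as scheduled | 744 | 150.9 | 3.02 |

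The 694 mL row allows for the second 0800h hormone and RNA draw being shared with the FSIGT, which starts at the same hour: 4 × (6 × 12.5 + 96) + 10 = 694 mL. On that reading the hormone draws alone would be 4 × 60 = 240 mL, just under the limit. The FSIGT samples alone exceed it either way.

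**Assessments 2 and 3.** 2 × 183.5 = 367 mL falls across these two visits, already more than the stated total for the study.

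Screening bloods are not counted in any row, so the whole-study figures are lower bounds.

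**The case against.** The strongest reply is that a qualifier is missing and the sum is not wrong. The sentence sits among remarks about needle insertion, catheter discomfort and care of the site, which describe a single inpatient stay. The limit fits one stay well, at 37 to 39 teaspoons. That is probably how the figure arose. It does not rescue the sentence, which calls the amount a total. The same section marks visit scope where it intends it, for example for pregnancy testing and dim lighting. Even on the per-visit reading, no cumulative volume is given anywhere.

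Other parts of the reply stand and limit what can be claimed:

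- The documents contain no blood-volume limit that 744 mL or 367 mL would breach, and the draws are spread over about 19 weeks. Nothing here shows that the schedule is unsafe.
- The minimal-risk statement refers to the risk section as a whole and does not cite the blood volume. It cannot be said to depend on this figure.
- The consent form is not among the documents reviewed, so what participants were actually told is not known. The ethics board had the full sampling schedule in the same application.
- The exact total depends on whether the second 0800h draw is shared with the FSIGT, and on the unstated screening volume.

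**Conclusion.** The concern holds: the sentence is wrong as written. Taken at its word, it understates the scheduled volume about threefold: under 246 mL stated, against 744 mL scheduled, or 694 mL if the second 0800h draw is shared with the FSIGT, in both cases before screening bloods. The conclusion rests on the volumes and time points in Procedures, on four complete assessments, and on a teaspoon of 4.93 to 5 mL. No choice within those ranges brings the whole-study total below 2.7 times the limit.

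The finding concerns disclosure only. It does not bear on the outcomes, sample size, randomisation or analysis, and it makes no judgement on whether the volume is acceptable. It should be corrected.

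**What to change.** Reconcile Potential Study Risks with the hormone, transcriptomic and FSIGT parts of Procedures:

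1. State the volume per assessment and for the whole study, computed from the schedule. As the schedule stands, that is about 184 mL (37 teaspoons) at each of four assessments, about 194 mL (39 teaspoons) at the first, and about 744 mL (151 teaspoons) in all, plus screening.
2. Give the screening volume and include it in the total.
3. Say whether the second 0800h hormone and RNA draw is separate from the FSIGT sampling, and adjust the figures if it is not.
4. State that assessments 2 and 3 are about two weeks apart and together draw about 367 mL.
5. Have the investigator confirm that the statement about recovery from the loss still applies to the corrected volumes and spacing.
6. Check the consent form for the same sentence and align it if it is there.

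The cost is a wording change in the risk section, and in the consent form if it carries the figure, submitted as a modification. The stated volume becomes less favourable. The modification form lists the study as in progress, with 32 of a planned 40 participants enrolled, so the correction can still reach anyone enrolled after it.
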